6.6.2 Clinical Laboratory Parameters

All laboratory results up to the end of treatment visit will be presented in standardized units. Grading of laboratory values will be assigned programmatically per the NCI CTCAE v5.0. The highest post-baseline grade will be presented for each lab test. Shift tables comparing the highest post-baseline to baseline CTCAE grade may be presented.

In addition, clinical laboratory data may be presented graphically for selected lab tests, by scheduled visit.

Laboratory values will be listed with grade per CTCAE and flagged when values are outside the normal reference range.

6.6.3 Deaths

The number of total deaths, deaths that occur within 30 days of last study treatment, and deaths that occur more than 30 days after last study treatment as well as the relationship to disease will be summarized. In addition, cause of death will be displayed in MedDRA preferred term (unless otherwise specified) and summarized. Death information will be listed by patient.

6.6.4 Concomitant Medications

Concomitant medications will be summarized by the World Health Organization (WHO) drug substance name. The number and percentage of patients taking concomitant medications may be tabulated for the following, but not limited to:

- Granulocyte-Colony Stimulating Factor (G-CSF)

Concomitant medications will be listed by patient.

6.6.5 Other Safety Analyses

6.6.5.1 Vital Signs

Vital sign measurements will be listed by patient for each time point. Summary statistics of vital signs and change from baseline may be tabulated where appropriate.

6.6.5.2 ECOG Performance Status

ECOG performance status will be summarized for each visit. Shifts from baseline to the lowest and highest post-baseline score may be tabulated.

6.6.5.3 ECG

ECG status (normal, abnormal clinically significant, or abnormal not clinically significant) may be summarized for each scheduled and unscheduled ECG, and shifts from baseline may be tabulated.

6.7 Additional Analyses

6.7.1 Pharmacokinetics and Immunogenicity Analyses

LV (ADC), total antibody, and MMAE concentrations will be summarized with descriptive statistics at each PK sampling time point. Selected PK parameters for LV, total antibody, and MMAE will be estimated by noncompartmental analysis and summarized using descriptive statistics. These data may be combined with PK data from other clinical trials with LV for population PK and exploratory exposure-response analyses.

The incidence of ATA will be summarized using the safety analysis set.

6.7.2 Biomarkers

Relationships of biomarker parameters (e.g., baseline values, absolute and relative changes from baseline) to efficacy, safety, and pharmacokinetic parameters will be explored.

Relationships and associated data that are determined to be of interest will be summarized. Details will be described separately in the Biomarker Analysis Plan.

7 INTERIM ANALYSIS

Interim analysis for futility will be performed separately for each cohort after at least 12 subjects of a given cohort have been treated and are efficacy evaluable post-baseline. Enrollment to each cohort may be held after 12 subjects for interim futility analysis of the respective cohorts.

The Bayesian predictive PPoS approach will be used to determine the futility criteria (Lee 2008). At the time of each interim analysis, the PPoS will be calculated. PPoS is the probability of achieving “success” should the cohort be continued to the maximum sample size of 30 given the data observed at interim, and a cohort is considered “success” if the posterior probability that the ORR exceeds the response rate of current standard of care (i.e., 15% for SCLC, 10% for NSCLC-squamous, 15% for NSCLC-nonsquamous, 10% for HNSCC, 10% for esophageal-squamous, and 15% for gastric and GEJ adenocarcinoma) is greater than 90%.

The ORR observed at interim will be counted as a response for the calculation of PPoS. Table 7-1 summarizes the PPoS based on the number of responses observed among the first 12 subjects.

Table 7-1: PPoS based on responses among the first 12 subjects

No. of responses ^a among the first 12 subjects	Predictive Probability of Success					
	SCLC (p ₀ =15%)	NSCLC-squamous (p ₀ =10%)	NSCLC-nonsquamous (p ₀ =15%)	HNSCC (p ₀ =10%)	Esophageal-squamous (p ₀ =10%)	gastric or GEJ adenocarcinoma (p ₀ =15%)
0	0.05%	0.2%	0.05%	0.2%	0.2%	0.05%
1	2%	8%	2%	8%	8%	2%
2	16%	36%	16%	36%	36%	16%
3	45%	73%	45%	73%	73%	45%
4	77%	94%	77%	94%	94%	77%
5	94%	100%	94%	100%	100%	94%

p₀ is the response rate of current standard of care of each cohort

a Including both confirmed and unconfirmed CR or PR observed at interim

If the PPoS is <10% (i.e., ≤ 1 response among the first 12 subjects), the data indicates that it is unlikely the ORR will be better than the response rate of current standard of care at the end of the cohort given interim results and the cohort could be stopped early due to insufficient activity. On the other hand, if the PPoS is >90%, the data suggests that if the same trend continues, there is a high probability to conclude a “success” at the end of the cohort. The PFS and OS will also be evaluated at the time of the interim analysis. Based on the efficacy and safety data, together with the PPoS, a cohort may be stopped early by the sponsor.

The predictive probability method allows the PPoS be computed at any interim time and provides flexibility in monitoring treatment activity continuously after the initial interim analysis.

In addition to the interim analysis for futility, interim data from the study may be presented at scientific meetings such as the annual meetings of the ASCO and the European Society for Medical Oncology.

8 CHANGES FROM PLANNED ANALYSES

8.1 Changes from the Original Protocol

Not Applicable.

8.2 Changes from the Original SAP

Not Applicable.

Appendix A IMPUTATION OF PARTIALLY UNKNOWN ADVERSE EVENT DATES

The algorithm below should be used to impute adverse event (AE) start dates for which only partial information is known. The algorithm should be applied to every AE record on a record by record basis. AE start dates should be imputed before imputation of AE condition end date in all cases. The AE condition end date should only be used in the imputation of the AE start date if it is a full known date.

Incomplete Start Date: If AE condition end date* is not missing, and the imputed start date is after the end date, the start date will be set to the AE condition end date.

AE day and month are missing

If the year is the same as the year of first dose of any study treatment:

AE start date will be imputed as the first dose date of any study treatment

If the year is before the year of first dose of any study treatment:

AE start date will be imputed as December 31st

If the year is after the year of first dose of any study treatment:

AE start date will be imputed as January 1st

AE month only is missing

Treat day as missing and replace both month and day according to the above procedure

AE day only is missing

If the month/year is the same as the month/year of first dose of any study treatment:

AE start date will be imputed as the first dose date of any study treatment

If the month/year is before the month/year of first dose of any study treatment:

AE start date will be imputed as the last day of the month

If the month/year is after the month/year of first dose of any study treatment:

AE start date will be imputed as the first day of the month

* only use condition end date if known and full end date is available.

Incomplete Stop Date: Within a single record, if the imputed stop date is before the start date, then the imputed stop date will be equal to the start date.

If AE outcome is “not recovered/resolved”, “unknown”, or blank: AE condition end date will not be imputed.

If AE outcome is “recovering/resolving”, “recovered/resolved”, “recovered/resolved with sequelae”, or “fatal” apply the following:

AE day and month are missing

If the year is equal to the year of the last dose date:

AE condition end date will be imputed as the minimum of (last dose date + 30, death date, data extraction date, December 31st of the end date year)

If the year is not equal to the year of the last dose date:

AE condition end date will be imputed as the minimum of (death date, data extraction date, December 31st of the end date year)

AE month only is missing

Treat day as missing and replace both month and day according to the above procedure

AE day only is missing

AE condition end date will be imputed as the minimum of (death date, data extraction date, last day of the end date month/year)

Example

AE Number 4: Condition/Event NAUSEA

First dose date 02APR2012

Prior to imputation

Log Line	Start date	Condition end date	Severity	Outcome
1	25APR2012	UNAPR2012	2	recovering/resolving
2	UNAPR2012	04MAY2012	1	recovered/resolved

Post imputation

Log Line	Start date	Condition end date	Severity	Outcome
1	25APR2012	30APR2012	2	recovering/resolving
2	02APR2012	04MAY2012	1	recovered/resolved

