5.4 Data Transformations and Derivations

5.4.1 General

Reported age in years will be used; if not available, age at informed consent in years will be calculated with the SAS® INTCK function (with method specified as “continuous”) using informed consent date and birth date.

Time variables based on two dates (e.g., Start Date and End Date) will be calculated as (End Date – Start Date +1 [in days]) unless otherwise specified in the planned analysis section.

Specifically, Study Day will be calculated as (Date–First Dose Date+1) for dates on or after the first dose date. The date of first dose will be Study Day 1. For dates prior to the first dose date, Study Day will be calculated as (Date–First Dose Date). For example, the date before the first dose date will be Study Day -1.

The following unit conversion will be implemented unless otherwise specified:

$$\text{Months} = \text{Days} / 30.4375$$

$$\text{Years} = \text{Days} / 365.25$$

Unless otherwise specified, baseline values used in all analyses will be the most recent non-missing measurement prior to the first dose of study drug.

The end-of-treatment (EOT) date will be the date the EOT visit is performed; if an EOT visit is not performed then the EOT date will be either the end-of-study (EOS) date or 30 days after the last dose of any study drug, whichever is earlier.

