6.6.1.1 Adverse Events of Special Interest (AESI)

Adverse events of peripheral neuropathy are considered AEs of special interest. Other AEs may also be added as AESI, as necessary.

Time to AE onset and time to resolution may be analyzed for treatment-emergent AESI, as appropriate. Patient level time to AE onset and time to resolution will be analyzed by cohort using Kaplan-Meier methodology. Treatment-emergent AESI outcomes will be tabulated. Only patients with treatment-emergent AESI events will be included in these analyses.

Time to onset of treatment-emergent AESI is defined as time from the date of first dose to start date of first treatment emergent AESI.

A treatment-emergent AESI is considered as resolved if the AESI has outcome of recovered/resolved or recovered/resolved with sequelae. For patients with multiple treatment-emergent AESI events, patient level resolution is defined as all treatment-emergent AESI events are resolved as defined above. Patient level time to resolution is defined as time from onset of first treatment-emergent AESI to the time of resolution of all treatment-emergent AESI events (i.e., end date of last resolved AESI event). Patients who do not have resolution for treatment-emergent AESI events will be censored at the date of last follow up.

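### SAP Appendix A imputes each AE log line in isolation, so a follow-on severity line with a partial start date can be dated before the event it continues

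*SAP*

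**What the plan says.** SAP Appendix A sets the unit of imputation: "The algorithm should be applied to every AE record on a record by record basis". Its rules for a partial start date on or after first dose are:

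- Only the day missing, same month and year as first dose: "AE start date will be imputed as the first dose date of any study treatment".
- Only the day missing, a later month: "AE start date will be imputed as the first day of the month".
- Day and month missing, same year as first dose: the first dose date. In a later year: 1 January.

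The one check on the result is an upper limit from the same record. When the end date is fully known and "the imputed start date is after the end date, the start date will be set to the AE condition end date". No rule looks at other lines of the same AE number.

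The appendix closes with a worked example headed "AE Number 4: Condition/Event NAUSEA", with "First dose date 02APR2012". Line 1 is Grade 2, starts 25APR2012, has a partial April end date and is recovering/resolving. Line 2 is Grade 1, has a partial April start, ends 04MAY2012 and is recovered/resolved. After imputation, line 1 ends 30APR2012 and line 2 starts 02APR2012.

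SAP 5.5 gives two uses for imputed AE dates: event duration and treatment-emergent status. SAP 6.6.1.1 names peripheral neuropathy as the AESI and defines time to onset as "time from the date of first dose to start date of first treatment emergent AESI". Patient-level time to resolution runs from that onset. Both analyses are optional.

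**The concern.** The two example lines share an AE number. The grade falls from 2 to 1, the outcome moves from recovering to recovered, and the second end date is the later one. Read naturally, line 2 is the same nausea after it improved. The printed result therefore has the improvement starting 23 days before the event it improves on. A programmer who follows the example will reproduce this.

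The error runs in one direction: onset too early, duration too long. It matters most for peripheral neuropathy. Protocol 7.6.1.1 requires changes in AE severity to be recorded. Protocol 7.6.1.3 allows neuropathy to be followed to resolution, return to baseline or study closure. Follow-on lines are to be expected for that event, and it is the one whose onset and resolution times may be reported.

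**Working it through.** **Inputs.** From the Appendix A example: first dose 02APR2012; line 1 start 25APR2012 (known) and end UNAPR2012; line 2 start UNAPR2012 and end 04MAY2012 (known). From SAP 5.4.1: "Time variables based on two dates (e.g., Start Date and End Date) will be calculated as" end minus start plus 1 day, and Study Day is date minus first dose date plus 1.

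**Reproducing the SAP's result.**
- Line 1 end: only the day is missing, so it is the earliest of death date, data extraction date and last day of the month. With no earlier death or extraction date, that is 30APR2012.
- Line 2 start: only the day is missing and the month is the first-dose month, so 02APR2012. The cap at 04MAY2012 does not bind.

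Both dates match the printed example.

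**Effect in the example.**

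| Quantity | From the known start of line 1 | After imputation of line 2 |
|---|---|---|
| Onset | 25APR − 02APR + 1 = Day 24 | 02APR − 02APR + 1 = Day 1 |
| Duration to 04MAY | 25APR to 04MAY = 10 days | 02APR to 04MAY = 33 days |

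Onset moves 24 − 1 = 23 days, and duration is 33 / 10 = 3.3 times as long. The 33 days is obtained both from line 2 alone and from the earliest start and latest end of the two lines. The imputed Grade 1 line also covers the whole Grade 2 line, 25 to 30 April, which is 6 days.

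**Later months.** As an illustration with assumed dates, take a line 1 start of 25 June and a line 2 start of UNJUN, with first dose in April. Line 2 becomes 1 June, which is 24 days before the event but not the first dose date. With only the day missing, a follow-on line can precede the event's onset only if both fall in the same calendar month, so the shift is at most 30 days. A larger shift needs the month to be missing too.

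**Effect of a lower bound in the example.**
- Bound by line 1's start: the later of 02APR and 25APR is 25APR2012. Line 2 lasts 10 days, the event starts on Day 24 and lasts 10 days. The Grade 1 and Grade 2 lines still overlap for the 6 days from 25 to 30 April.
- Bound by line 1's imputed end: line 2 starts 30APR2012 and lasts 5 days. The event again starts on Day 24 and lasts 10 days, and the overlap shrinks to 30 April itself.

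**The case against.** The strongest reply is that setting an unknown start to first dose is deliberately conservative for treatment-emergent status, one of the two uses named in SAP 5.5, and that little else depends on it. Much of this stands. The tables listed in SAP 6.6.1 are mainly incidence and maximum severity, with each patient counted once per term, and no AE-duration summary is listed. Time to onset is not among the uses named in SAP 5.5, so its dependence on imputed dates is an inference. The AESI timing analyses are optional and descriptive. The SAP computes no duration in its example and does not say how log lines of one AE are combined. Neither document says how often such partial dates occur.

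The conservatism argument does not cover this pattern, however. Line 1's known Day 24 start already makes the event treatment-emergent, so moving line 2 to Day 1 protects nothing. If the preceding line began before first dose, a later-of rule leaves the Appendix A date as it is.

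A reader might infer that every follow-on line with a missing day is sent back to Day 1. Appendix A does not say that: it happens only for a partial date in the first-dose month, or in the first-dose year with the month missing. A reader might also infer that the main safety tables are distorted. In the example, incidence, maximum grade and treatment-emergent status are the same with either date.

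**Conclusion.** Appendix A states a rule that can give a demonstrably wrong date, and its own example shows one: onset on Day 1 instead of Day 24, and a duration of 33 days instead of 10. This is more than a missing detail, but its reach is narrow: AE duration, and AESI time to onset and time to resolution if those are run. Efficacy results, including the confirmed response rate, are unaffected. It should be corrected before database lock but does not threaten the trial's conclusions.

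The figures rest on two assumptions. Line 2 is taken as the continuation of line 1, which the shared AE number, grades, outcomes and end dates support but the SAP does not state. Onset and duration are taken from line 2 itself or from the earliest start among the lines, since the SAP has no rule for combining them. The example is nausea, which is not a named AESI, so it shows how the rule behaves rather than the size of any AESI result.

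**What to change.** 1. Add to Appendix A: for the second and later log lines of one AE number, the imputed start is the later of the date given by the existing rules and the start date, known or imputed, of the preceding line. The cap at the record's own known end date still applies.
2. Derive AESI onset from the first treatment-emergent log line, not simply the first log line. SAP 6.6.1 counts worsening after first dose as treatment-emergent, and Protocol 4.2 excludes only ongoing neuropathy of Grade 2 or higher, so a Grade 1 line may predate dosing.
3. Correct the example so that line 2 starts 25APR2012.

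This bound fits Appendix A's order, in which starts are imputed before ends. It should not be presented as removing the two-grade overlap of 25 to 30 April. That would need line 2 to be bounded by line 1's end date instead.

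The cost is one or two sentences and a small programming change. SAP section 1 allows amendment before database lock.

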Appendix B IMPUTATION OF PARTIALLY MISSING SUBSEQUENT ANTICANCER THERAPY START DATE

The algorithm below should be used to impute subsequent anticancer therapy start dates for which only day is missing.

- If the month and year of the start date of subsequent anticancer therapy are the same as the month and year of a response assessment date, and
 - If the response is a PD, subsequent anticancer therapy start date will be imputed as the response assessment date or the day after the last study treatment, whichever is later.
 - If the response is not a PD, subsequent anticancer therapy start date will be imputed as the first day of the month or the day after the last study treatment, whichever is later.
- Else if the month and year of the start date of subsequent anticancer therapy are the same as the month and year of the end date of last study treatment, subsequent anticancer therapy start date will be imputed as the day after the last study treatment end date.
- Else if the start date of subsequent anticancer therapy is later than the end date of last study treatment based on available month and year, subsequent anticancer therapy start date will be imputed as the first day of the month.

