6.5. On treatment Response Assessments

Time points for radiographic exams for patients with RECIST v1.1 measurable tumor lesions or bone scan should be calendar based and do not depend on cycle visits. It is recommended that scans not be scheduled on the dosing day. It is recommended that scans done on the same day as Day 1 of subsequent cycles be completed and reviewed prior to infusion with LV.

The schedule of response assessments should not be adjusted for dose delays, dose interruptions, or other reasons for changes in the timing of a subject's study activities. Imaging should be conducted on the following schedule (Sections 6.5.1 and 6.5.2) until treatment is discontinued for any of the following reasons: disease progression, unacceptable toxicity, investigator decision, consent withdrawal, study termination by the sponsor, pregnancy, or death, whichever comes first. For all tumor cohorts, imaging should also be performed whenever disease progression is suspected.

6.5.1. For non-prostate cancer subjects (Cohorts 1–6, and 8):

- Every 6 weeks (± 3 days) for 12 months after the first dose of LV

- Every 12 weeks (± 7 days) thereafter

Objective responses (CR or PR) will be confirmed with repeat scans 4–6 weeks after the first documentation of response.

6.5.2. For prostate cancer subjects (Cohort 7):

- PSA assessment every 3 weeks (± 3 days) per calendar
- CT/MRI scan every 8 weeks (± 7 days) per calendar for the first 24 weeks, then every 12 weeks (± 7 days) thereafter
- Bone scan every 8 weeks (± 7 days) per calendar for the first 24 weeks, then every 12 weeks (± 7 days) thereafter

6.6. End of Treatment Visit (30 to 37 days after last dose of study drug)

Subjects will continue to receive LV until disease progression, unacceptable toxicity, investigator decision, consent withdrawal, study termination by the sponsor, pregnancy, or death, whichever comes first.

Regardless of time since last dose, EOT visits should be completed prior to administration of a new therapy. EOT visits should occur within 30 to 37 days after the last dose of LV unless delayed due to an AE. If EOT evaluations are completed before 30 days after the last study treatment, the subject will be contacted 30 to 37 days following the subject's last study treatment to assess for AEs and concomitant medications.

- Physical examination (Section 7.6.4), including weight
- Vital signs (Section 7.6.2)
- Pregnancy test for subjects of childbearing potential (see Section 7.6.5)

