5.4.2 Best Response

The determination of antitumor activity will be based on objective response assessments made by the investigator according to the RECIST v1.1 (Eisenhauer 2009). Only response assessments on or prior to start date of any new anticancer therapy will be considered for best response. The patient's best response will be the best demonstrated response to date that has been confirmed, when confirmation is required (i.e. for PR and CR only). The patient's best response will be used in determining the ORR.

A response (CR or PR) will be considered confirmed if the subsequent disease assessment conducted no earlier than 4 weeks after the initial response still shows CR or PR. A patient will have a best response of SD if there is at least one SD assessment (or better) ≥ 5 weeks after the start of treatment and the patient does not qualify for confirmed CR or PR. RECIST v1.1 outlines scenarios for best overall responses when confirmation of CR and PR is required.

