5.5 Handling of Dropouts and Missing Data

Missing data will not be imputed unless otherwise specified. Missing AE start date and/or end date will be imputed while calculating duration of events and treatment-emergent status (see Appendix A for imputation details).

For time-to-event endpoints, e.g., duration of response, time to response, PFS, and OS, patients who have no specific event will be censored as specified for each respective endpoint in Section 6.5.

Patients who do not have at least two (initial response and confirmation scan) post-baseline response assessments will be counted as non-responders for analysis of the primary endpoint.

Missing subsequent anticancer treatment start date will be imputed while deriving the time-to-event endpoints as applicable (see Appendix B for imputation details).

For prior therapies end dates, if month and year are present and only day is missing, day may be imputed. The imputed day will be the last day of the month if the prior therapy end date is earlier than the enrollment date based on the available month and year; the imputed day will be the day before enrollment if the prior therapy was stopped within the same month and year as enrollment. If month or year is missing, no imputation will be performed.

For prior therapies start dates, if month and year are present and only day is missing, day may be imputed. The imputed day will be the first day of the month. If month or year is missing, no imputation will be performed.

Unless otherwise specified, if the numeric value of a clinical laboratory test is not available because it is below the lower limit of quantification (LLOQ), “< LLOQ” should be used whenever applicable. In cases where a numeric value is required, e.g., calculating the mean and standard deviation, the LLOQ/2 will be used for the calculation.

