6.5.2.2 Duration of Response (DOR)

DOR is defined as the time from the first documentation of objective response (CR or PR that is subsequently confirmed) to the first documentation of PD or death due to any cause, whichever comes first. PD includes radiologic evidence of tumor progression and clinical progression per investigator.

Patients who are not evaluable or have a response of SD or better per RECIST v1.1 at the same visit as investigator claim of clinical progression will be counted as disease progression (i.e., an event). The date of progression will be the date of investigator claim of clinical progression or PD date per RECIST v1.1, whichever is earlier.

DOR data will be censored as described below:

- Patients who do not have PD and are still on study at the time of an analysis will be censored at the date of last disease assessment documenting absence of PD.
- Patients who have started a new anticancer treatment prior to documentation of PD will be censored at the date of last disease assessment prior to the start of new treatment.
- Patients who are removed from the study prior to documentation of PD will be censored at the date of last disease assessment documenting absence of PD.

DOR will only be calculated for patients who achieve a confirmed CR or PR.

DOR will be analyzed by cohort using the Kaplan-Meier methodology and Kaplan-Meier plots will be provided. The median DOR and its 2-sided 90% CI will be calculated as appropriate.

Sensitivity analyses will be performed for DOR to evaluate the robustness of treatment effects:

- A sensitivity analysis will be performed by censoring deaths or PD per RECIST v1.1 occurring after two or more missed visits at the last disease assessment;
- Another sensitivity analysis will be performed by counting PD or Death which occurred after start of new anti-cancer as events;
-

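### SAP Appendix B dates a partly missing new-therapy start from the same-month scan result, so DOR and PFS keep every PD scan but lose off-treatment non-PD scans; the effect on ORR is left unstated

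*SAP*

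**What the plan says.** SAP Appendix B covers subsequent-therapy start dates with only the day missing. If a response assessment falls in the same month, there are two branches:

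- PD: "If the response is a PD, subsequent anticancer therapy start date will be imputed as the response assessment date"
- CR, PR or SD: "If the response is not a PD, subsequent anticancer therapy start date will be imputed as the first day of the month"

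Both branches carry the same floor: "or the day after the last study treatment, whichever is later". If the month holds both a PD and a non-PD scan, both branches apply and no order between them is given.

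The imputed date feeds the censoring rule for DOR in SAP 6.5.2.2, which SAP 6.5.2.3 carries over to PFS: "Patients who have started a new anticancer treatment prior to documentation of PD will be censored at the date of last disease assessment prior to" that treatment's start.

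Best response has its own filter in SAP 5.4.2: "Only response assessments on or prior to start date of any new anticancer therapy will be considered for best response". Confirmation there requires that a "subsequent disease assessment conducted no earlier than 4 weeks after the initial response still shows CR or PR". SAP 5.5 adds: "Patients who do not have at least two (initial response and confirmation scan) post-baseline response assessments will be counted as non-responders". SAP 5.5 and Protocol 9.3.1.3 invoke the imputation of this date for time-to-event endpoints. Neither mentions ORR.

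On the order of events, Protocol 6.6 says: "Regardless of time since last dose, EOT visits should be completed prior to administration of a new therapy". The EOT visit includes CT/MRI unless a scan was done in the previous 4 weeks. Under Protocol 6.7, follow-up scans after stopping treatment without progression end when new therapy begins.

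**The concern.** A date that decides whether a scan is admitted should not be derived from what the scan showed. If sites follow Protocol 6.6 and 6.7, an EOT or follow-up scan in the month of new therapy came before that therapy. Appendix B assumes this order when the scan shows PD and usually reverses it when the scan does not.

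The consequence for DOR and PFS is one-sided. A subject with PD at such a scan contributes an event. A subject shown to be event-free at the same scan is censored at the assessment before it. Events stay in the numerator while event-free follow-up leaves the risk set, which pulls the Kaplan-Meier estimates down. If the same date were also applied to best response, a valid confirmation could be refused and the primary endpoint would be affected.

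**Working it through.** **The plan's own figure.** SAP 5.2 gives 90% exact intervals for confirmed ORR at N=30. The Clopper-Pearson limits are the 5% quantile of Beta(x, 31−x) and the 95% quantile of Beta(x+1, 30−x). For x = 3, 6, 9, 12, 15 they are 2.8–23.9%, 9.1–35.7%, 16.6–46.5%, 25.0–56.6% and 33.9–66.1%. The table is reproduced and not in dispute; it is used below for size.

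**The date rule.** Let S be the scan date, L the last dose and M the first of the month, with S in the month of new therapy.

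- PD: imputed start = max(S, L+1)
- Non-PD: imputed start = max(M, L+1)
- A scan is kept if S ≤ imputed start (the wording of SAP 5.4.2)

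For PD, max(S, L+1) is never before S, so no PD scan is discarded. For non-PD, the scan is kept only if S = M or S ≤ L+1. Running every scan day of a 30-day month:

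| Days from last dose to scan | Non-PD discarded | PD discarded |
|---|---|---|
| −10, −1, 0, 1 | 0 of 30 | 0 of 30 |
| 2, 7, 14, 21, 30, 33, 37 | 29 of 30 | 0 of 30 |

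The last row includes the 30 to 37 day EOT window of Protocol 6.6. The one survivor is a scan on the 1st. The DOR and PFS rule counts assessments before the start, not on it. Read strictly, a scan on the imputed start date (the 1st, or the day after last dose) would be lost there too, so 29 of 30 is the lenient count.

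**Dated examples.** PR on 10 March, next scan 21 April (21 + 21 = 42 days later), new therapy in April with day unknown:

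| Last dose | Scan on 21 April | Imputed start | PFS |
|---|---|---|---|
| 7 April | PR | max(1 April, 8 April) = 8 April | censored 10 March |
| 24 March | PR | max(1 April, 25 March) = 1 April | censored 10 March |
| 7 April | PD | max(21 April, 8 April) = 21 April | event 21 April |

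The first two subjects lose 42 days of event-free follow-up. The third, in the same position, is an event. As a counter-example, with last dose 15 June and a non-PD scan on 10 June, the imputed start is 16 June and the scan is kept.

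**If the imputed date is also used in SAP 5.4.2.** The PR on 21 April falls after 8 April (or 1 April), the response is unconfirmed, and the subject counts as a non-responder. Each such loss costs 1/30 = 3.3 points. For example, 6/30 = 20.0% (90% CI 9.1–35.7) becomes 5/30 = 16.7% (6.8–31.9).

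**How many subjects.** The documents give no frequencies. Assumed ranges: 10–20% start new therapy without prior PD, 10–30% of those dates lack the day, and 30–50% of those have a scan in that month.

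- Low: 0.10 × 0.10 × 0.30 = 0.3%, or 0.09 per 30 subjects
- High: 0.20 × 0.30 × 0.50 = 3.0%, or 0.9 per 30 subjects
- Over the 180 subjects in this SAP (5.2): 180 × 0.003 = 0.5 to 180 × 0.03 = 5.4

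These count any same-month scan, on or off treatment. For lost responders, multiply first by the 10–50% ORR range in SAP 5.2: 0.09 × 0.10 = 0.009 to 0.9 × 0.50 = 0.45 per cohort. That is before requiring that the scan be off treatment and the only confirming scan.

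**The case against.** A reader might infer that the rule removes confirmed responders from the primary endpoint. The documents do not say so. SAP 5.5 and Protocol 9.3.1.3 apply the imputation to time-to-event endpoints, the SAP default is no imputation unless specified, and 5.4.2 does not cite Appendix B. In favour of the inference, the opening line of Appendix B is unrestricted, 5.4.2 needs a start date, no other rule supplies one, and DOR is calculated only in confirmed responders. So the ORR route is a plausible reading of a gap, not a stated rule.

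A reader might also infer that every same-month non-PD scan is lost. The last-dose floor prevents that: scans taken on treatment, or the day after the last dose, are kept under the on-or-prior wording. Most confirmations probably occur on treatment, since treatment continues until progression or another listed reason.

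The true order is not certain either. Protocol 6.6 says the EOT visit should come first, not that it must. The EOT scan can be waived, and Protocol 7.2 has standard-of-care imaging recorded in the CRF as well. Declining to credit the study drug with a scan that might follow new therapy is a defensible conservative choice. But that caution applies equally to a PD scan, which the rule always keeps.

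Finally, for DOR and PFS the SAP plans a sensitivity analysis that counts PD or death after new therapy as events. It does not restore the event-free scans or make the imputed date independent of the result. The interim futility count includes unconfirmed responses, so a lost confirmation would not change it.

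**Conclusion.** The concern holds for DOR and PFS. Within its stated scope, Appendix B keeps every same-month PD and drops nearly every off-treatment same-month non-PD scan, against the order that Protocol 6.6 and 6.7 set out. Each affected subject is censored one assessment early: 6 weeks on the first-year schedule, 12 weeks after that, less where the lost scan fell outside the schedule. On-treatment scans are not affected.

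For ORR the finding is an omission: the SAP does not say which date 5.4.2 uses when the day is missing. If it is the imputed one, a responder could be lost, at 3.3 points per subject for N=30.

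The likely numbers are small: about 0.1 to 0.9 per cohort of 30 with any same-month scan, and only a small subset of those as lost responders. All three input ranges are assumptions, and the argument about order assumes that sites follow the protocol. The point deserves correction because the dependence on outcome is built into the rule and is cheap to remove, not because a large shift is expected.

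**What to change.** Replace both same-month branches of Appendix B with one rule that ignores the scan result. Impute the start as the latest of (a) the first of the month, (b) the day after last study treatment and (c) the day after the last protocol-scheduled response assessment in that month, PD or not, capped at month end. This also settles months that hold both a PD and a non-PD scan.

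In SAP 6.5.2.2 and 6.5.2.3, let assessments on or prior to the imputed start count for censoring, as 5.4.2 already does for best response. Without this, a scan on the last day of the month would equal the capped start and still be lost. State in 5.4.2 that it uses the same imputed date.

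In the first example, the start becomes 22 April and the 21 April scan is kept whether it shows PR or PD.

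The cost is a few sentences in a SAP amendment before database lock, with no new data. The downside is that a scan in fact taken after new therapy began could occasionally be credited. A sensitivity analysis using the current first-of-month rule would cover that.
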